### **8.1.7 Sleep diary**

The Sleep Diary is composed of seven generic, patient-reported questions that assess sleep concepts of relevance and importance to adults who report sleep disturbance due to asthma.

The Sleep Diary features two subjective, patient-rated items that use a 0-to-10 NRS to assess sleep quality and feeling rested upon awakening (ie, restorative sleep). Additional items include the patient-estimated initial sleep attempt time and sleep onset time, number of nighttime awakenings after sleep onset, total time spent awake after sleep onset, and wake time the next day. Participants are instructed to complete all questions upon awakening each day. All questions except the one about restorative sleep ask participants to recall "last night"; question about restorative sleep asks participants to recall "when they got up for the day today". Items about sleep quality and restorative sleep are scored; the other items are reported/described separately, as appropriate for each item.

[figure not shown]
The participants will complete the items of the Sleep Diary daily, as per SoA (see [Section 1.3](#)).

Science37 Metasite: For the completion of the baseline and postbaseline assessments, refer to Appendix 7 ([Section 10.7](#)).

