16. SIGNATURE PAGE

Client:	SANOFI
Protocol Number:	LPS16677
Document Description:	Final Statistical Analysis Plan
SAP Title:	A Phase 4, randomized, double-blind, placebo-controlled, multicenter, parallel-group study of the effect of dupilumab on sleep disturbance in patients with uncontrolled persistent asthma
SAP Version Number:	2.0
Effective Date:	24 FEB 2022
Author(s):	
	
Approved by:	
	
	

ADDENDUM TO STATISTICAL ANALYSIS PLAN FOR LPS16677

The SAP was approved in February 2022. Due to data issues detected during the course of the study, this addendum provides additional data handling rules not included in the SAP approved.

#1 In [Section 15.8](#) of SAP: Handling rule of duplicates records for daily questionnaires

There are many duplicate records for daily questionnaires remotely completed by phone (Asthma sleep disturbance questionnaire/sleep diary/ANS/ADSD). The duplicates (same participant, question, date, but with different time/answer provided) will have to be managed at ADaM level.

The rule to select the most appropriate record is as the followings:

1. To select the most frequently recorded response for a given patient/question/day.
2. If it does not enable to identify a unique response (eg, 2 different answers submitted 2 times), then the earliest submission (based on recorded time) will be selected.

#2 In [Section 15.8](#) of SAP: Handling of Sleep Diary Data

Sleep diary is one of the PRO questionnaires in LPS16677 with the following questions:

- 1: Select the number that best describes the quality of your sleep last night
- 2a: Approximately what time did you start trying to fall asleep last night?
- 2b: Approximately what time did you fall asleep last night?
3. Approximately how many times did you wake up last night (not including when you woke up for the day today)? Record “0” if you do not remember waking up last night.
4. Considering all the times you woke up last night, how much time were you awake in total? Record “0” if you do not remember waking up last night.
- 5: At what time did you wake up for the day today?
6. Select the number that best describes how rested you felt when you got up for the day today.

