During the ongoing blinded data review, illogical/inconsistent responses to these questions have been identified within the same participant and questionnaire submission. For example, time falling asleep is recorded to occur before trying to fall asleep, time waking up is recorded to occur before time of falling asleep, total sleep time is recorded as being longer than the time in bed, etc.

In order to remove the illogical responses in the derivation of sleep related endpoints, the following rules will be applied:

- A. For questions related to previous night (2a and 2b), if the recorded time lies between 12:00 and 23:59 then set the date equal to the day before the questionnaire was completed. Otherwise set date equal the day questionnaire was completed.
- B. Additionally, the following conditions will be checked:
 1. “Date/Time Did You Wake Up Today” must be equal or later than “Date/Time Fall Asleep Last Night”
 2. “Date/Time Did You Wake Up Today” must be later than “Date/Time Try Fall Asleep Last Night”

3. “Date/Time Did You Wake Up Today” minus “Date/Time Fall Asleep Last Night” must be equal or greater than WASO which is “Time awake after initial sleep onset but before the final awakening” and is the response to Question 4.
4. “Date/Time Fall Asleep Last Night” must be equal or later than “Date/Time Try Fall Asleep Last Night”
5. WASO is equal or greater than zero.

If any of the above conditions fail, then the data collected on that day will not be considered in the derivations.

Once the above rules are applied, the following parameters will be derived (except for WASO which is collected directly from the questionnaire) and used for analysis:

WASO = Wake After Sleep Onset = Time awake after initial sleep onset but before the final awakening

#3 The team noted some typo in PROMIS conversion table (raw-score to t-score) in the [section 15.8](#) of SAP for LPS16677 – Morpheo study.

Please see corrections below:

- Raw-score = 9 => t-score = 35.2
- Raw-score = 37 => t-score = 73.4
- Raw-score = 40 => t-score = 80.1

#4 In [section 8.1.4](#), it is indicated that SCS rescue medications will be identified using CDGsn00010. The medical team discussed this point, and finally decided to use ATC code to identify SCS from rescue medication page (Asthma Reliever page) to keep consistency with [section 15.10](#) (ie, CDGsn00010 will finally not be used).

#5 Asthma Control Questionnaire ( and ACQ-5) in [section 15.3](#):

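### The SAP addendum's sleep-diary checks put no upper limit on the wake time, so one entered 12 hours late is kept and lengthens any duration derived from it

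*SAP*

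**What the plan says.** Addendum item #2 gives its purpose as follows: "In order to remove the illogical responses in the derivation of sleep related endpoints, the following rules will be applied". It works in two steps.

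- **Rule A** assigns dates to the two bedtime items only. It begins "For questions related to previous night (2a and 2b), if the recorded time lies between 12:00 and 23:59 then set the date equal to". Clock times from noon onwards thus go to the preceding day, and all others to the completion day. It does not mention question 5, the wake-time item ("At what time did you wake up for the day today").
- **Conditions B1 to B5** are then checked.
  - B1, against sleep onset: "Date/Time Did You Wake Up Today” must be equal or later than “Date/Time Fall Asleep Last Night".
  - B2, against the attempt to sleep: "Date/Time Did You Wake Up Today” must be later than “Date/Time Try Fall Asleep Last Night".
  - B3: wake time minus sleep onset "must be equal or greater than WASO" (wake after sleep onset, question 4).
  - B4: onset is not before the attempt to sleep.
  - B5: WASO is not negative.

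If any condition fails, that day's data are left out of the derivations. Diary parameters are then derived from what remains, except WASO, which is taken as answered.

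Two other places bear on this. Protocol section 8.1.7 fixes when the diary is filled in: "Participants are instructed to complete all questions upon awakening each day". Addendum item #1 shows that submission times are held, since ties among duplicate records are resolved by time: "then the earliest submission (based on recorded time) will be selected".

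**The concern.** The stated purpose is to remove illogical responses. A diary completed on waking cannot truthfully report a wake time that lies hours after its own submission, yet nothing in B1 to B5 detects this. B1 and B2 are order checks. B3 is a minimum-duration check, which also limits the wake time only from below. A night with an impossible length therefore stays in the data and enters the participant's average.

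At stake is the credibility of diary durations such as total sleep time, which the addendum itself names among its examples of inconsistent data. These are averaged over few enough nights for one such entry to dominate a participant's value.

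**Working it through.** **Inputs**

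- Rule A and B1 to B5: Addendum item #2.
- Averaging windows: up to 28 days after baseline (SAP section 8); Day -6 to Day 1 at baseline, with at least 4 measurements (SAP section 4.4.6).
- Assumption 1: question 5 is dated to the completion day. No date rule is stated, but the item asks about today.
- Assumption 2: sleep time = wake − onset − WASO. The derivation formulas are not legible in the public document.

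The plan gives no figure of its own to reproduce.

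**One night.** Attempt 22:30, onset 23:00, WASO 30 min.

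| Wake time entered | Wake − onset | B1–B5 | Sleep time |
|---|---|---|---|
| 07:00 (true) | 480 min | all pass | 480 − 30 = 450 min (7.5 h) |
| 19:00 (12 h late) | 1200 min | all pass | 1200 − 30 = 1170 min (19.5 h) |

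The difference is 1170 − 450 = 720 min.

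**A grid of nights.** Bedtimes 21:00 to 02:00 in 15-min steps (21), latencies of 15, 30 and 60 min (3) and wake times 05:00 to 10:00 in 30-min steps (11), with WASO 30 min, give 21 × 3 × 11 = 693 nights. Each clock-time error was applied alone.

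| Error | Passes B1–B5 |
|---|---|
| Wake time 12 h late | 693 of 693 |
| Attempt time off by 12 h, true bedtime at or after midnight | 297 of 297 (adds 720 min of latency) |
| Attempt time off by 12 h, true bedtime before midnight | 0 of 396 |
| Onset time off by 12 h | 3 of 693 |
| Wake time 3 h too early | 671 of 693 |

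The first row is algebra rather than evidence of frequency: adding 720 min to a quantity that has only lower bounds can never make it fail.

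**Effect on one participant's mean.** One late wake time adds 720/28 = 25.7 min to a full 28-night mean, 720/7 = 102.9 min to a 7-night baseline, and 720/4 = 180 min to a baseline with the minimum 4 nights.

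**Effect on an arm mean.** With about 130 participants per arm (protocol synopsis), one such night moves the arm mean by 25.7/130 = 0.2 min, or the arm's mean baseline by 102.9/130 = 0.8 min.

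**Side effect on B3.** With onset at 23:00, a WASO of 600 min fails when wake is 07:00 (480 < 600) but passes when wake is 19:00 (1200 ≥ 600).

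**The case against.** The strongest reply concerns reach, and most of it stands.

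- The named diary secondary endpoints (nocturnal awakenings, sleep quality, restorative sleep, WASO) are direct answers, and the primary endpoint comes from a separate questionnaire. None is computed from the wake time.
- Formal testing covers only the primary endpoint, awakenings and the PROMIS T-score (SAP section 8.2.13). Derived diary durations receive nominal p-values.
- The documents do not say how often such entries occur, how times are keyed in, or whether the device blocks a future time. The inconsistencies that the addendum cites from blinded review concern order and duration.

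A reader might infer three stronger things that the documents do not support.

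- **That the rules delete errors that shorten the night and keep those that lengthen it.** This is not a general property. A wake time 3 h too early, which shortens the night, passes in 671 of 693 cases. A 12-hour error in sleep onset is rejected in 690 of 693, and the 3 that pass shorten sleep.
- **That the WASO endpoint is corrupted.** A wrong wake time does not change the recorded WASO. The looser B3 matters only if the same diary also holds an impossible WASO, which means two errors on one night.
- **That the treatment comparison is biased.** The same rules apply blind to both arms. What is shown is added noise and distorted levels.

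What the reply does not remove is the gap itself: by their own stated purpose, the rules keep a response that cannot be true.

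**Conclusion.** The point holds as a minor but real gap in data cleaning. B1 to B5 accept a wake time 12 h late, and each accepted entry adds exactly 720 min to any diary parameter built on wake minus onset for that participant-night.

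The result rests on question 5 being dated to the completion day. If Rule A were also applied to question 5, against its wording, the 19:00 entry would move to the previous evening and fail B1, B2 and B3. It also rests on a true wake time before noon and on at least one derived parameter using wake minus onset. The names of those parameters are not legible, although total sleep time is the obvious candidate.

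**What to change.** Add a condition B6 to Addendum item #2: the question 5 wake date and time must not be later than the recorded date and time of the submission from which that answer was taken. State the date rule for question 5 at the same time. Because Addendum item #1 selects the most frequent answer question by question, say which submission counts when several carry the chosen answer.

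On a B6 failure, exclude only the parameters that use the wake time. The existing consequence drops the day's data, which read literally would also discard valid awakenings, sleep quality, restorative sleep and WASO from a night where only the wake time is wrong.

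Optionally, add a ceiling on attempt-to-wake time, set on blinded data, as a secondary screen. It is not complete: with an illustrative 16-hour ceiling, 27 of the 297 after-midnight attempt-time errors in the grid still pass.

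The cost is one or two lines of derivation code on data already held. B6 needs no chosen threshold, whereas the optional ceiling does. A few more nights will be missing for the derived parameters, and late wake times in diaries completed late in the day will not be caught.

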8.2. Secondary and Tertiary/Exploratory Efficacy Endpoints

The secondary and tertiary efficacy endpoints associated with "Change from baseline" (except [REDACTED], due to limited sample size) will be analyzed using the MMRM model in the same fashion as for the analysis of the primary endpoint (see [Table 2-2](#)) with the baseline values corresponding to the outcome variables. Adjusted LS means for each study intervention group, LS mean difference between the Dupilumab and placebo groups, and the corresponding SEs and 95% CIs will be provided for all endpoints (and p-value corresponding to the LS mean difference provided at Week 12 only). However, formal statistical testing will be performed only for the number of nocturnal awakenings and PROMIS t-score that will be performed in the frame of the hierarchical procedure considered to account for multiplicity issues (nominal two-sided p-value provided for descriptive purpose only for other secondary and tertiary endpoints).

Further definitions of endpoints are included in [Section 15.8](#) and [Section 15.9](#).

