8.2.1. Sleep diary

In addition to MMRM model, the number of nocturnal awakenings, sleep quality, restorative sleep, [REDACTED] WASO and [REDACTED], all based on sleep diary data, will be summarized at baseline and each post-baseline visit (Week 4, Week 8, and Week 12).

The number of nocturnal awakenings will be determined based on the answer on the question 3 from the sleep diary: "Approximately how many times did you wake up last night (not including when you woke up for the day today)?"

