8.2.13. Multiplicity issues

In order to handle multiple primary or secondary endpoints, the overall Type-I error will be controlled by the use of a hierarchical inferential approach:

- Statistical significance of the primary analysis at the 0.05 alpha level will be required before drawing inferential conclusions about first secondary endpoint
- Inferential conclusions about successive secondary endpoints will require statistical significance of the prior one.

Hierarchical testing will be performed in the same order as described below:

1. Change from Baseline to Week 12 in the Asthma Sleep Disturbance Questionnaire (primary endpoint)
2. Change from Baseline to Week 12 in the average number of nocturnal awakenings (first secondary endpoint)
3. Change from Baseline to Week 12 in PROMIS t-score

This fixed hierarchical approach will ensure a strong control of the overall Type-I error rate at the 0.05 level.

Additional endpoints (secondary or tertiary) that are not included in the hierarchical testing procedure will not be formally tested (i.e., nominal p-value provided for descriptive purpose only).

9. Safety Analysis

All safety results will be summarized using the Safety analysis set by actual study intervention group.

The observation periods include:

- The **pre-treatment** period is defined as the time from the signed informed consent date up to first administration of the IMP.
- The **treatment-emergent adverse event** (TEAE) period is defined as the time from the first administration of the IMP (on Day 1) to the last administration of the IMP + 84 days or until the participant switches to commercialized dupilumab or other biologics
- The **post-treatment** period is defined as the time starting 1 day after the end of the TEAE period up to the end of the study follow-up.

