The Sleep Diary features two subjective, participant-rated items that use a 0-to-10 NRS to assess sleep quality and feeling rested upon awakening (i.e., restorative sleep). Additional items include the participant-estimated initial sleep attempt time and sleep onset time, number of nighttime awakenings after sleep onset, total time spent awake after sleep onset, and wake time the next day. All questions except the one about

restorative sleep ask participants to recall “last night”; question about restorative sleep asks participants to recall “when they got up for the day today”. Items about sleep quality and restorative sleep are scored; the other items are reported/described separately, as appropriate for each item.

The following variables will be derived from sleep diary:

WASO (min)= Time awake after initial sleep onset but before the final awakening

This is data collected from Question 3 of the Sleep Diary: “Considering all the times you woke up last night, how much time were you awake in total?”

[REDACTED]
[REDACTED]
[REDACTED] [REDACTED] [REDACTED]

Sleep diary data will be directly provided by CLARIO.

[figure not shown]
Asthma Control Questionnaire ([REDACTED] and ACQ-5)

[REDACTED] collects participants assessment of their asthma during the previous week based on 6 questions on a 7-point scale (0 = no impairment to 6 = maximum impairment).
[REDACTED]

The ACQ was designed to measure both the adequacy of asthma control and change in asthma control which occurs either spontaneously or as a result of study intervention. The [REDACTED], with the first 5 items assessing the most common asthma symptoms (corresponding to ACQ-5):

1. frequency in past week awoken by asthma during the night
2. severity of asthma symptoms in the morning
3. limitation of daily activities due to asthma
4. shortness of breath due to asthma
5. wheeze

[REDACTED]
[REDACTED]
[REDACTED]

A global score is calculated as follows:

[figure not shown]
Higher score indicates lower asthma control. Participants with a score below 1.0 reflect adequately controlled asthma and participants with scores above 1.0 reflect inadequately controlled asthma. On the 7-point scale of the [REDACTED], a change or difference in score of 0.5 is the smallest change that can be considered clinically important, corresponding to the Minimal Clinically Important Difference (MCID) defined by the developer. The participants will complete the [REDACTED] as per SoA.

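### Do SAP Addendum items #1, #2 and #7 leave open which sleep-diary answers and which duplicate records are analysed?

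*SAP*

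**What the plan says.** Addendum item #2 amends the sleep-diary part of SAP Section 15.8. It lists the diary questions (1, 2a, 2b, 3, 4, 5, 6) and reports that blinded review found impossible combinations of times within single submissions. It sets date rules and five checks, introduced with "In order to remove the illogical responses in the derivation of sleep related endpoints". It then states: "If any of the above conditions fail, then the data collected on that day will not be considered in the derivations". The next sentence says that "the following parameters will be derived (except for WASO which is collected directly from the questionnaire"; in the public copy only WASO is visible after it. Item #2 defines WASO and adds "and is the response to Question 4".

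Three other places bear on scope:

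- Section 15.8 introduces the variables derived from the diary, shows WASO, and says of it: "This is data collected from Question 3 of the Sleep Diary".
- Section 8.2.1 says: "The number of nocturnal awakenings will be determined based on the answer on the question 3 from the sleep diary".
- Section 8.2 says that "formal statistical testing will be performed only for the number of nocturnal awakenings and PROMIS t-score", and Section 8.2.13 places second in the hierarchy "Change from Baseline to Week 12 in the average number of nocturnal awakenings (first secondary endpoint").

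On duplicates, item #1 covers the remotely completed daily questionnaires and names them, including the Asthma Sleep Disturbance Questionnaire. It takes the most frequent answer per participant, question and day, and the earliest submission if there is no unique answer. Item #7 takes the earliest record for a participant and date, and names no questionnaire.

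**The concern.** The exclusion sentence in item #2 names no diary items. If it means the whole diary day, an error in a bedtime entry removes that night's awakenings count, sleep quality and restorative sleep, none of which enters a check. Awakenings are formally tested and gate the PROMIS t-score. If inconsistent entries cluster on bad nights, the retained nights understate awakenings, more so in the arm with more bad nights, and the treatment difference shrinks. The WASO label in Section 15.8 (Question 3) coincides with the awakenings item in Section 8.2.1, which adds to the doubt.

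Items #1 and #7 can return different values for the same day, and item #1 names the primary questionnaire, so an unsettled choice would reach the primary endpoint. Item #1 also works question by question. If it runs before the item #2 checks, it can assemble a night that the participant never submitted.

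**Working it through.** **1. Which items the checks use**

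| Check | Diary items |
|---|---|
| 1 | 5, 2b |
| 2 | 5, 2a |
| 3 | 5, 2b, 4 |
| 4 | 2b, 2a |
| 5 | 4 |

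Items 1 (quality), 3 (awakenings) and 6 (feeling rested) appear in none. The observation about scope is correct.

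**2. What the exclusion sentence most naturally covers**

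- Item #2 amends Section 15.8, whose diary text speaks of derived variables and visibly shows WASO. Awakenings are not derived there. Section 8.2.1 reads them straight from an answer.
- The sentence after the rule names WASO as the one listed parameter that is collected directly. Awakenings, quality and restorative sleep are also collected directly, so they would not fit that list.
- Those three endpoints are printed openly in SAP Table 2-1, Section 6.2.1 and Section 8.2.1. Had they been on the list, they would probably be visible. This is inference, not proof.

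On this narrow reading no awakenings count is lost.

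**3. Size if the literal reading were programmed**

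The documents give no failure rate, so these inputs are assumed: mean awakenings 1.5 and 1.0 per night (true difference 0.50), participant rates gamma with shape 1, 2 or 4, nightly counts Poisson, 28 nights (SAP Section 8), 200,000 simulated participants per arm. Failure probability is set low at 1 awakening or fewer, high at 3 or more, and midway at 2. Standardised ratio = difference ratio / √(variance ratio).

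| Failure low / high | Difference ratio (shape 1 / 2 / 4) | Variance ratio | Standardised ratio |
|---|---|---|---|
| 20% / 20% | 1.00 / 1.00 / 1.00 | 1.007 / 1.014 / 1.025 | 0.997 / 0.993 / 0.988 |
| 3% / 10% | 0.992 / 0.988 / 0.982 | 0.987 / 0.980 / 0.976 | 0.998 / 0.998 / 0.994 |
| 3% / 20% | 0.978 / 0.964 / 0.954 | 0.966 / 0.946 / 0.932 | 0.995 / 0.991 / 0.988 |
| 5% / 30% | 0.965 / 0.944 / 0.927 | 0.946 / 0.914 / 0.892 | 0.992 / 0.987 / 0.981 |

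The worst case turns 0.50 into 0.927 × 0.50 = 0.46 awakenings per night. Its standardised effect is 0.927 / √0.892 = 0.981, a loss of 1.9%.

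Baseline needs at least 4 measurements (SAP Section 4.4.6). With 12 or 11 pre-baseline records, the binomial probability of fewer than 4 usable is 0.006% or 0.02% at 20% failure, 1.5% or 2.9% at 40%, and 7.3% or 11.3% at 50%.

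**4. Item #1 against item #7**

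- With two records they always agree (0 of 25 answer patterns on the 0-4 scale).
- With three they differ when the second and third agree with each other but not with the first: 5 × 4 = 20 of 125 patterns. Answers 3, 2, 2 give 2 under #1 and 3 under #7.
- With four they differ in 200 of 625.

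For three records with independent error e per submission, spread evenly over the four wrong answers:

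P(differ) = e(1−e)² + (1−e)e²/4 + 12(e/4)³

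This gives 0.046, 0.083 and 0.138 for e = 5%, 10% and 20%.

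A one-point discrepancy on one night moves a 28-day mean by 1/28 = 0.036 and a seven-record baseline by 1/7 = 0.143. If 5-20% of nights had three submissions, the mean absolute discrepancy per night runs from 0.05 × 0.046 × 1 = 0.002 to 0.20 × 0.138 × 2 = 0.055. The upper figure equals a participant's shift only if every discrepancy has the same sign. With random signs over 28 nights the mean absolute shift is about 0.040, and the average shift is about zero. Neither rule uses treatment arm.

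**5. The assembled night**

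Take bedtime/onset submissions of 23:00/23:10, 23:30/23:40 and 23:30/23:45, with wake time 06:30 and WASO 20 minutes in each. All three pass. Question-by-question selection gives bedtime 23:30 (majority) and onset 23:10 (earliest, because all three differ), which fails check 4. This needs three differing submissions on one night and selection before checking, an order the addendum does not state.

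**The case for a change.** The best case for a change is that two programmers could follow the same text and build different datasets for a formally tested endpoint. Nothing written excludes the literal reading, because the lead-in speaks broadly of sleep-related endpoints. Duplicates are not rare: the addendum itself says there are many, and item #1's own example is a four-record day. No minimum number of post-baseline diary days is set, so lost nights would pass unnoticed. A clarifying clause costs almost nothing.

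Some of this stands. The scope of item #2, the precedence between #1 and #7, and the order of selection and checking are all unwritten. The inference drawn from them is weaker. If item #7 governed the daily questionnaires, item #1's first step would never take effect, so #1 must be the rule for the questionnaires it names and #7 the rule for other same-day records. Full literalism about item #2 would sweep in every questionnaire answered that day, which nobody proposes; the context that limits it to the diary also points to the time-based variables.

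Nor is retaining the awakenings answer plainly better. Question 4 asks about the same awakenings that Question 3 counts, and impossible times suggest careless entry. Dropping such a submission under a rule set in blinded review is defensible, and so is keeping the count.

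**Conclusion.** The concern describes the wording correctly, but no change follows. The gap in item #2 is one that analysts fill sensibly from Sections 15.8 and 8.2.1, and on that reading the awakenings endpoint is untouched. Precedence between #1 and #7 follows from what each rule says it covers. The Question 3 label for WASO in Section 15.8 is a clerical slip: that section prints the time-awake question itself, and item #2 already assigns WASO to Question 4. Whether to keep counts from inconsistent submissions, and whether to select duplicates by question or by whole submission, are trade-offs without a clear winner.

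The likely effect is very small. On the literal reading the awakenings difference falls by 1-7% and its standardised effect by 0.2-1.9% when failures concentrate on bad nights; random failure on 20% of nights leaves the difference unbiased and adds 0.7-2.5% to the variance. Item #2 does not touch the primary endpoint, and the duplicate rules can differ there only on days with three or more submissions. All these sizes rest on assumed failure, error and duplicate rates, because the documents give none. Only failure on some 40-50% of nights, combined with the literal reading, would cost a noticeable share of baselines (1.5-11%).
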